3.4.2 Exclusion Criteria

- 1) Unable to provide informed consent (e.g. impaired cognition or judgment).
 - 2) Evidence of a medical condition that might alter results or compromise the interpretation of results, including active infection, kidney failure, severe liver dysfunction, severe respiratory or cardiac failure.
 - 3) Evidence of severe hematologic abnormality including severe anemia and/or thrombocytopenia.
 - 4) Electrically powered implants (e.g. cochlear implants, neurostimulators) that might be susceptible to radio frequency interference.
 - 5) Unable to completely avoid acetaminophen for duration of study.
 - 6) History of adverse reaction to glucagon (including allergy) besides nausea and vomiting.
 - 7) Established history of allergy or severe reaction to adhesive or tape that must be used in the study.
 - 8) Use oral (e.g. thiazolidinediones, biguanides, sulfonylureas, glitinides, DPP-4 inhibitors, SGLT-2 inhibitors) anti-diabetic medications.
 - 9) Any investigational drug use within 30 days prior to enrollment.
 - 10) Pregnant or lactating females.
 - 11) History of more than one episode of DKA and/or severe hypoglycemia within the six months prior to study enrollment.
 - 12) Current history of sub-optimally treated nausea and/or vomiting.
 - 13) Parents/guardians or subjects who, in the opinion of the Investigator, may be non-compliant with study schedules or procedures.
-

- 14) Current and sustained use of insulin formulation (delivered via pump) not approved/advised to be used in the Tandem t:slim pump.

Subjects that do not meet all the enrollment criteria may not be enrolled. Any violations of these criteria must be reported in accordance with IRB Policies and Procedures.

4 STUDY PROCEDURES

Table 1: Schedule of Study Procedures (page *x*) provides a tabular view of the following information.

4.1 Recruitment Procedures

A study staff member will review the potential subject's medical health record to determine eligibility for the study based upon inclusion/exclusion criteria. When identified, the prospective participants and designated contacts will be briefed by a study staff member by phone, email, or during clinic visits regarding the study procedure and the inclusion and exclusion criteria. Subjects may also be informed about the study by internal and external recruitment methods (i.e., CHOP Congenital Hyperinsulinism Center newsletter, Congenital Hyperinsulinism International newsletter, Pediatric Endocrine Society newsletter). Potential subjects and contacts will be sent an informed consent document by mail, fax, or email, or will be given the consent form during their clinic visit.

4.2 Consent Procedures

Once potential subjects and/or parents/guardians have had time to review the consent document, they will speak with a study physician who can further explain the study and answer any questions the subject and/or parent/guardian may have. The subject will then complete the informed consent process with a study physician, should the subject desire to participate in the study. Study staff will answer any questions that the subjects may have during their participation. They will share any new information in a timely manner that may be relevant to the subject's willingness to continue participating in the trial. The subjects and/or parents/guardians may choose to discontinue their participation at any time without prejudice.

4.3 Experimental Procedures and Data Collection

4.3.1 Screening Visit

- After informed consent is obtained, all subjects will have a screening visit to confirm eligibility.
 - The subject will be interviewed and the case report form will be completed by study staff to establish whether the subject is eligible to continue with the screening according to inclusion/exclusion criteria, in the event the medical record review provided outdated data.
 - Demographic/medical history data to be recorded:
 - Age
 - Sex
 - Race and ethnicity
-

- Date of HI diagnosis
- Date of pancreatectomy and percentage removed
- Date of diabetes diagnosis/insulin initiation
- Medical, surgical, and social history, allergies, and review of systems relevant to inclusion and exclusion criteria
- Medications (prescription and non-prescription)
- Duration of insulin pump use
- Type of insulin used in pump
- Average total daily dose of insulin in the last 30 days (from pump history, as available – for comparison with insulin dosing during the standard care and bionic pancreas arms of the study)
- Usage of CGMS, if any (type of CGMS, days per month worn, usage of data, whether insulin is dosed based on CGMS alone, alarm settings)
- Physical examination
- Vital Signs: height, weight, temperature, blood pressure, heart rate, respiratory rate
- Pregnancy test (for female subjects 11 years and older)
- Safety laboratory tests: CBC, CMP, hemoglobin A1c
- Once all the laboratory results have been returned, a study physician will review the case report form to determine subject eligibility to continue in the study. If subjects are not eligible to continue in the study, the results of abnormal tests will be reported to the subjects.
- Subjects who have been screened and are eligible can participate without having to be rescreened for a period of one year. The study staff should obtain verbal confirmation that there have been no health events that would make them ineligible if the interval between screening and participation is longer than 3 months.
- Upon confirmation of eligibility and participant’s willingness to continue, subjects will be assigned to an order of admissions based upon a randomized, crossover design. There will be a minimum of 1 week time between admissions.
- Pediatric subjects will be required to have a parent or guardian accompanying them during the inpatient admissions.

4.4 Standard Care Admission

A 4-day inpatient admission in which subjects will continue their home insulin regimen. Blood glucose data will be collected from finger-stick and from CGMS during the study.

4.4.1 Run-in period (Day 0)

- Medical history
 - Prior/concomitant medications
 - Vital signs: height, weight, temperature, blood pressure, heart rate, respiratory rate
 - Standardized diabetic diet
 - Insulin administered via insulin pump per home regimen
 - Placement of Dexcom® CGMS for BG monitoring
-

- Blood glucose check by finger-stick before breakfast, before lunch, before dinner, at bedtime, and at 03:00am. PRN blood glucose checks may occur at the discretion of the study physician(s)
- Initiation of telemetric monitoring of CGMS connectivity
- Adverse event monitoring

4.4.2 Days 1-3

- Vital signs: temperature, blood pressure, heart rate, respiratory rate every 12 hours (appx.)
- Standardized diabetic diet
- Insulin administered via insulin pump per home regimen. Subjects will be asked to change their insulin infusion set and reservoir at least every two days, just as they will during the bionic pancreas arm
- Study staff confirms CGMS is running
- Dexcom® calibration twice daily (before breakfast and dinner). Calibration will be delayed if there is a steep rise or fall in the blood glucose or if there has been carbohydrate intake in the last 30 minutes. If a calibration is delayed for any of these reasons, it will be performed at the next opportunity.
- Blood glucose check by finger-stick before breakfast, before lunch, before dinner, at bedtime, and at 03:00am. PRN blood glucose checks may occur at the discretion of the study physician(s)
- Telemetric monitoring of CGMS connectivity
- Adverse event monitoring

4.4.3 Discharge

Subjects will be discharged on the fourth day of the admission.

4.5 Bihormonal Bionic Pancreas Admission

Study staff at CHOP will undergo thorough in-person training on all functions of the Bionic Pancreas System by the device's developers from Massachusetts General Hospital. Briefly, this training will constitute application and removal of the BP to a human subject, operating and overseeing the BP system daily functioning, filling and priming the pumps, understanding the information and settings on the BP's display screen, using the meal bolus feature, and troubleshooting of expected and unexpected issues. Our colleagues at Massachusetts General Hospital will be available throughout the study to respond to questions, concerns, and comments.

The bihormonal pancreas will be placed upon admission and there will be 1 day run-in period. This will be followed by 3 days of data collection for comparison with the data obtained from the standard of care during the Control Admission. Following this, the patient will transition back to their home regimen and will be discharged home.

4.5.1 Run-in Period (Day 0):

- Medical history
 - Prior/concomitant medications
 - Vital signs: height, weight, temperature, blood pressure, heart rate, respiratory rate
-

- Standardized diabetic diet
- Insulin administered via insulin pump per home regimen until transition to the BP
- Placement of Dexcom® CGMS for BG monitoring
- Blood glucose check by finger-stick before breakfast, before lunch, before dinner, at bedtime, and at 03:00am. PRN blood glucose checks may occur at the discretion of the study physician(s).
- Initiation of telemetric monitoring of CGMS connectivity
- The study staff will place the two infusion sets, fill and prime one Tandem® t:slim™ pump with insulin and one Tandem® t:slim™ pump with glucagon and label all pieces appropriately
- The control algorithm will be initialized only with the subject weight
- Diagnostics will be performed to ensure that the CGMS device is appropriately calibrated and that all of the components of the bionic pancreas (Dexcom® G5® Platinum AP, iPhone® running the control algorithm, Tandem® t:slim™ infusion pumps) are in good communication with each other
- The subject's own insulin infusion pump will be stopped and disconnected, and its infusion set will be removed
- The staff will start the bionic pancreas as close as possible to a minute divisible by 5 minutes (i.e. on a 5-minute mark) and before 4:00 PM.
- We will initiate bionic pancreas control with a glucose target of 110 mg/dL to 130 mg/dL, according to the Investigator's discretion. Study physician(s) reserve the right to adjust the subjects' glucose targets to a value between 110 mg/dL and 140 mg/dL (inclusive), according to Investigator's discretion.

4.5.2 Days 1-3

- Vital signs: temperature, blood pressure, heart rate, respiratory rate twice daily
 - Standardized diabetic diet
 - Study staff confirms CGMS is running
 - Blood glucose check by finger-stick before breakfast, before lunch, before dinner, at bedtime, and at 03:00am. PRN blood glucose checks may occur at the discretion of the study physician(s).
 - CGMS calibration twice daily (before breakfast and dinner). Calibration will be delayed if there is a steep rise or fall in the blood glucose (>2 mg/dL/min), there has been carbohydrate intake in the last 30 minutes, or there has been a glucagon dose in the last 15 minutes. In the immediate aftermath of carbohydrate intake or glucagon dosing it is possible for BG to be rising without a change in interstitial fluid glucose. If a calibration is delayed for any of these reasons, it will be performed at the next opportunity. Additional calibrations may be performed if the CGMS is inaccurate relative to a BG measurement as long as it is not calibrated within 30 minutes of food intake or 15 minutes of glucagon dosing. Extra calibrating will not be performed if the CGMS is within 15 mg/dL when the BG is ≤ 75 mg/dL and within 20% if the BG is >75 mg/dL at times when the rate of change is low.
-

- Telemetric monitoring of CGMS connectivity. Alarms will sound if the CGMS glucose is less than 50 mg/dL. The first step for all glucose-related alarms will be to perform a fingerstick BG measurement. If the BG measurement is not consistent with the fact that a threshold alarm has occurred:
 - The staff will assess the possibility of a compression artifact. If a compression artifact is suspected, steps to relieve the pressure on the transmitter will be taken. If no compression is suspected, the CGMS will be calibrated as long as there has been no carbohydrate intake in the last 30 minutes, no glucagon dosing in the last 15 minutes, and there is no steep rise or fall in glucose (>2 mg/dL/min). If a calibration is delayed for this reason, it will be performed at the next opportunity.
 - If the BG measurement is consistent with a low threshold alarm, the hypoglycemia will be treated with carbohydrate ingestion according to the usual practice. The staff will investigate the glucagon infusion set and consider replacing it.
 - The first step in responding to hyperglycemia according to the CGMS will be to perform a fingerstick BG measurement. If the BG measurement is not consistent with the CGMS, the CGMS will be calibrated as long as there has been no carbohydrate intake in the last 30 minutes and there is no steep rise or fall in glucose (>2 mg/dL/min). If a calibration is delayed for this reason, it will be performed at the next opportunity. If the BG measurement is consistent with the CGMS, the insulin infusion site will be investigated and replacement will be considered.
 - If there is a complete failure of bionic pancreas operation and it is anticipated that restarting it will take more than an hour, subjects may take over their own BG control using their own insulin pump or with insulin injections until the bionic pancreas can be brought back online with the help of study staff. During the day, this should be rare. If the failure occurs at night, every effort should be made to correct the problem as soon as possible, which should almost always be possible within 12 hours.
 - If a CGMS sensor fails during the course of an experiment, the system will provide basal insulin based on past requirements and will allow announcement of meals and entry of fingerstick BG measurements, which will be treated as CGMS data and may result in administration of insulin and/or glucagon. The CGMS sensor will be replaced as soon as possible and normal bionic pancreas control will resume when the new sensors is calibrated.
 - Subjects will be asked to announce the three major meals of the day, but not snacks, to the bionic pancreas. The meal announcement will consist of choosing the type of meal (breakfast, lunch, dinner) and the size of the meal relative to typical meals for that subject (snack, smaller than typical, typical, larger than typical).
 - The insulin infusion set and reservoir will be changed at least every two days.
-

- The glucagon reservoir will be replaced every day. Each reservoir will be filled with two vials of freshly reconstituted Lilly glucagon. The glucagon infusion set will be changed daily with the reservoir change.
- On days when both the insulin and glucagon reservoirs will be changed, they will be changed at different times in the day, separated by at least one hour. The infusion sets and tubing will be labeled to avoid confusion or cross connection.
- All episodes of hypoglycemia, carbohydrate interventions, any nausea and/or vomiting, any other adverse events, time spent exercising, and any unscheduled infusion set changes, alcohol use, etc. will be recorded.
- Adverse event monitoring.
- At the end of the 4-day period, subjects will return the bionic pancreas.

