The GUI can also be used to manage meal boluses as usual, and will administer correction boluses in response to entered BG values, during periods when the Dexcom® CGM is offline, such as the period after a sensor is replaced and before the new sensor has been calibrated. During these times the control algorithm will determine and direct the administration of insulin basal rates either based on the subject's weight early in the experiment, or on the average of adaptively determined basal rates for that time of day once sufficient experience has been accumulated (i.e. 24 hours or more) by the control algorithm. The controller will also administer insulin and/or glucagon as appropriate in response to any entered BG values, just as if they were Dexcom® CGM values.

The GUI also displays local audio and visual alarms if communication is dropped between the Dexcom® CGM transmitter and the bionic pancreas control unit or between the control unit and the two insulin pumps. The Dexcom® CGM also has its own hard-coded alarm

distinct from the bionic pancreas when the CGM glucose crosses below 55 mg/dl. These alarms may be configured so that they require the entry of a code to dismiss.

The iPhone® communicates wirelessly via the Bluetooth Low Energy (BTLE) protocol with up to two Tandem® t:slim™ insulin pumps to deliver insulin and glucagon.

In all configurations, if communication failures between the Dexcom® CGM and the bionic pancreas or the bionic pancreas and the cloud are not resolved within 15 minutes they trigger alerts to study staff who will then contact the wearer according to study protocol. If communication failure between the bionic pancreas and pumps is not resolved within 15 minutes this triggers and alert to study staff who will contact the wearer. Also in both configurations, if the Dexcom® CGM glucose drops below 50 mg/dl and the user does not enter a BG into the bionic pancreas GUI within 15 minutes, this will trigger an alert to study staff, who will then contact the wearer according to the study protocol. Monitoring will be the same in all study arms.

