7.2.3 Continuous Glucose Monitoring System

During each admission, a Dexcom® G5® continuous glucose monitor system (CGMS) will be placed to measure glucose concentration continuously. The CGMS will be calibrated twice daily before breakfast and dinner and as requested by the CGMS. During Control Admission, the CGMS will be connected to an iPhone® to allow remote monitoring. During Experimental Admission, the CGMS will be part of the bionic pancreas system and will provide input to the controller. The sensor is powered by the battery within the transmitter that clips to the sensor and the whole assembly is held to the skin with an adhesive patch and communicates wirelessly with the CGMS receiver. If the CGMS sensor fails for any reason during the experiment it will be replaced promptly.

Prior to any reuse of the CGM transmitter between patient admissions, study staff will thoroughly clean and disinfect the transmitter according to the manufacturer's best practices (detailed instructions included in the Dexcom® User Guide).

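### Sensor recalibration after a discordant fingerstick, and the compression check, are written only for the bionic pancreas admission, which allows a treatment-linked measurement difference, mainly in time below 60 mg/dL

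*Combined protocol and SAP*

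**What the plan says.** **Bionic pancreas admission (4.5.2).** Besides the twice-daily calibrations, the section gives three responses to a sensor that disagrees with a fingerstick:

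- Optional extra calibration: "Additional calibrations may be performed if the CGMS is inaccurate relative to a BG measurement", outside set windows after food or glucagon. A tolerance limits it: "Extra calibrating will not be performed if the CGMS is within 15 mg/dL when the BG is ≤ 75 mg/dL", or within 20% at higher BG, when glucose is changing slowly.
- After a low alarm that the fingerstick does not confirm, staff first consider a compression artefact and relieve it if suspected. Otherwise, "If no compression is suspected, the CGMS will be calibrated as long as there has been no carbohydrate intake in the last 30 minutes", with further conditions on glucagon timing and rate of change.
- After a high reading: "If the BG measurement is not consistent with the CGMS, the CGMS will be calibrated as long as there has been no carbohydrate intake", again with a rate-of-change condition.

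**Standard care admission (4.4.2).** The section provides for "calibration twice daily (before breakfast and dinner"), with similar reasons for delay. Extra fingersticks are allowed at the study physician's discretion but are not linked to recalibration. There is no tolerance, compression check or calibration after an unconfirmed reading.

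**Text covering both admissions.** Section 7.2.3 says "The CGMS will be calibrated twice daily before breakfast and dinner and as requested by the CGMS", and connects the control-admission CGMS to a phone "to allow remote monitoring". Section 7.2.2 describes the sensor's own alarm, "distinct from the bionic pancreas when the CGM glucose crosses below 55 mg/dl", and states that monitoring does not differ between arms.

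**Endpoints.** Section 6.1 takes both co-primary outcomes, mean glucose and time below 60 mg/dL over the last three days, from this CGMS in both admissions.

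**The concern.** The same sensor is the outcome instrument in both admissions, but the written rules for correcting it differ by admission. A false reading can be cut short under 4.5.2 and has no matching rule under 4.4.2. Measurement error could then depend on treatment, and a paired comparison does not remove that.

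Time below 60 mg/dL is the exposed outcome because it rests on few readings. The results are also meant to size a larger study (6.5.2, 6.6), so a treatment-linked difference would carry forward.

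**Working it through.** **1. Reference difference.** Section 6.6 gives time below 60 mg/dL as 1.2% (SD 1.1) on the bionic pancreas and 2.8% (SD 1.2) on pump therapy, a difference of 1.6 points. With SD of the difference = sqrt(1.1² + 1.2² − 2r × 1.1 × 1.2), a paired t-test, 80% power and alpha 0.05 (two-sided assumed), all eight sample sizes in 6.6.2 reproduce. For example, r = 0.001 gives SD 1.627 and n = 11; r = 0.5 gives SD 1.153 and n = 7. These inputs are therefore the plan's own yardstick.

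**2. In minutes.** Readings come every 5 minutes (6.5.2).

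- 3 days × 288 = 864 readings = 4,320 min.
- 1 point = 43.2 min.
- 1.6 points = 0.016 × 4,320 = 69 min.

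**3. Where the tolerance meets the endpoint.** Lower limit of an acceptable reading under 4.5.2:

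| BG (mg/dL) | Rule | Lower limit (mg/dL) |
|---|---|---|
| 70 | BG − 15 | 55 |
| 75 | BG − 15 | 60 |
| 75 | 0.80 × BG | 60 |
| 80 | 0.80 × BG | 64 |

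At BG 75 both limits equal the endpoint threshold. A stable reading below 60 with BG above 75 is always out of tolerance, so it is open to correction under 4.5.2 and has no matching rule in 4.4.2. The rule does not catch every false low: at BG 70, a reading of 55 to 60 is within tolerance and would stand even if the rule applied to both admissions.

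**4. Scale.** The documents give no frequency or duration of sensor artefacts and no response time. Assume 15 minutes of false low, left uncorrected in standard care only.

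- One subject: 15/4,320 = 0.35 points.
- Mean of 10, one subject affected: 0.035 points (0.035/1.6 = 2.2% of the reference difference).
- Mean of 10, every subject affected: 0.35 points (0.35/1.6 = 22%).
- Staff calibrate alike in both admissions: 0.

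**5. Against sampling error.** The standard error of the paired difference at n = 10 is 1.627/√10 = 0.51 (r = 0.001) or 1.153/√10 = 0.36 (r = 0.5). The one-subject case is about 7% to 10% of a standard error; the all-subjects case is about 67% to 95%.

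**6. Mean glucose.** If those three readings are wrong by 50 to 100 mg/dL (assumed), the subject's mean moves by 3 × 50/864 = 0.17 to 3 × 100/864 = 0.35 mg/dL. Even if this happened in every subject, it is at most 0.35/30 = 1.2% of the 30 mg/dL reference difference.

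**The case against.** The strongest reply is that these are silences rather than conflicting rules. Extra calibration under 4.5.2 is optional, and 4.4.2 does not forbid it. Section 7.2.2 makes monitoring common to the arms, and 9.3.3 and 9.3.4 rely on monitoring in standard care. Part of the 4.5.2 text has an operating purpose, because the sensor drives dosing there. Staff may well act the same way in both admissions. The fingerstick endpoints in the synopsis and 6.2 do not depend on CGMS calibration, and this is a convenience-sample pilot.

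Most of this stands, and it keeps the point minor. It does not close the gap: common monitoring governs detection and alerts, not what is done to the sensor once a fingerstick contradicts it. The operating purpose explains the fuller text without giving a reason for different outcome-measurement rules. Scheduled fingersticks, five a day, sample brief lows sparsely.

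Three stronger readings are tempting, and the documents do not support them:

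- **Low glucose goes undetected in standard care.** The alarm, remote connection and monitoring statement in 7.2.2 and 7.2.3 say otherwise.
- **The difference favours the bionic pancreas.** An uncorrected sensor can read falsely low and add time below 60, or read high and hide it.
- **The difference could never be examined.** The fingerstick schedule is the same in both admissions, MARD against meter values is planned (6.4.1), and 9.3.1 puts all data in one database. What is unspecified is a signed difference and reporting by admission. Section 9.3.1 names calibration data for the bionic pancreas device; its control-phase sentence neither includes nor excludes them.

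**Conclusion.** The asymmetry is in the text, and no section extends the sensor-correction steps to standard care. Following the plan as written allows a treatment-linked measurement difference in a co-primary outcome. It is a possible bias, not a demonstrated one, and its direction and size are unknown.

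The effect on time below 60 mg/dL runs from 0, if staff calibrate alike, through 0.035 points, if one subject in ten has 15 uncorrected minutes, to 0.35 points if all ten do. Frequency and duration are assumptions, so this range shows scale and does not bound the bias.

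A reader might infer a materially inflated false-positive rate. With no true effect, n = 10 and the SDs in 6.6, a constant 0.35-point shift would raise two-sided rejection from 5% to about 9% (r = 0.001) or 14% (r = 0.5). That requires the event in every subject, in standard care only and in the same direction, and nothing in the documents supports it.

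This is a minor point and a worthwhile clarification, held with medium confidence. It does not affect the sample-size tables.

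**What to change.** - In 4.4.2, apply the discordance tolerance, extra-calibration and compression-check steps already in 4.5.2, so that one set of sensor rules covers both admissions. Keep the glucagon-timing condition only where glucagon is given.
- In 9.3.1, state that calibrations are recorded in both admissions.
- In 6.4.1, report by admission the calibration count, MARD and the signed CGMS-minus-meter difference.

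The cost is a few sentences and a few descriptive rows, using fingersticks already planned. No new endpoint, visit or model is needed. The downside is slightly more CGMS handling in standard care.
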